pathways/proteins influenced by FMRP (the mitogen-activated protein kinase (ERK) and MMP-9) are biomarkers of treatment responsiveness. Because lovastatin is also an anti-inflammatory, we will characterize MEK/ERK signaling in peripheral immune cells both and pre- and post- treatment to determine whether levels of these signaling molecules are predictive biomarkers of treatment response. We hypothesize that those individuals with elevated inflammatory cytokine profiles will be most responsive to lovastatin treatment. Once modeled in FXS, results from these studies can then be applied to other neurodevelopmental disorders including Rasopathies.

Lovastatin as a treatment for FXS: Lovastatin is an inhibitor of the rate-limiting enzyme in cholesterol biosynthesis and an FDA-approved treatment for hyperlipidemia. Lovastatin has also been proposed as a treatment for IDD, particularly for Rasopathies and Neurofibromatosis Type 1 (NF1). Lovastatin reduces activation of the small guanosine triphophatase (GTPase) Ras, which in turn reduces activity of the MEK/ERK signaling pathway. Lovastatin interferes with recruitment of Ras to the membrane, a process required to transition from inactive GDP to active GTP. The interaction of Ras with the membrane requires the prost-translational addition of a farnesyl group to the C terminus of Ras, and lovastatin inhibits Ras farnesylation by targeting the upstream mevalonate pathway.

Recent extensions of animal studies to FXS have been promising. In a study of Fmr1 knock out (KO) mouse, intraperitoneal injections of lovastatin protected the mice from audiogenic seizures that are part of the FXS phenotype. In the KO mouse, the lack of FMRP represents a loss of the translational repressor for many proteins important for synaptic plasticity. Lovastatin corrected the excessive protein production in the KO mouse, inhibited RAS-ERK1/2 signaling in hippocampal neurons, and improved the phenotype. Although lovastatin has been used to treat children as young as one year of age, FDA approval extends only to 10- to 17-years-olds and studies of efficacy for cognitive impairments in NF1 have shown benefit and safety for this age range so this study will focus on the same age group.

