Randomization to lovastatin or placebo will be conducted by the UCDMC pharmacy using a computer algorithm. IDS will over-encapsulate the active study medications and prepare the placebo capsules prior to dispensing. Equivalence of the groups on these stratification variables, as well as other variables (e.g., child autism symptom severity and maternal IQ), will be tested, with any significant differences accounted for by inclusion of covariates in the primary analyses.

The dose will range from 10 to 40 mg of lovastatin or placebo depending on tolerance of the dose. The dose will start at 10 mg per day and will be increased by 10 mg increments on a weekly basis from study weeks 1 through 4 as listed below. Dosing will occur once per day in the evening. Dose tolerance will be assessed through a weekly phone call or email contact conducted by a study physician during the titration period and a dose decrease can be made if necessary. If a dose decrease is made between weeks 2 and 4 no further dose titrations will occur and subject will be considered on a stable dose throughout the remainder of the titration period and study.

If more than one dose change is needed, the subject will be discontinued from the study. Once a stable dose is reached, subjects will remain at the designated dose through visit 3 and will be contacted approximately every other week by study staff to assess for possible adverse events and verification of proper dosing. Study participants will be dispensed study medication at visits one and two and will discontinue dosing after completing visit 3.

Week 1: 10 mg (Day 1-7) Week 2: 20 mg (Day 8-14) Week 3: 30 mg (Day 15-21) Week 4: 40 mg (Day 22- 28) Week 5-20: 40 mg or OTD (Day 29- 140)

Our dosage model takes into consideration the biphasic and pleiotropic effects of statins. The biphasic effect can be explained by the higher affinity for the enzymes that catalyze non-sterol product formation than for the cholesterol biosynthesis enzymes. Low doses of statins mainly affect cholesterol synthesis, while high doses affect mevalonate-derivative intermediates, which are essential for the prenylation of proteins and Ras activation (Li, et al., 2007). The pleiotropic effects of statins suggest that the sustained use of statins (more than 2 weeks) causes PTEN up regulation, which inhibits the PIK3/AKT pathway; and that higher acute dose administration of statins will inhibit Ras, which is our targeted effect. (Ludman, et al., 2009).

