Adverse events (AE) will be documented along with any changes in study medication dose or use of other medications. Each AE will be scored for severity, frequency, and relatedness to lovastatin. All serious adverse events will be reported to our IRB as required by reporting guidelines. The DSMB will also review the study data and assess for safety on a regular basis.

Safety labs, listed below, will be conducted at all three visits through the UC Davis health system pathology laboratory. These laboratory tests will assess for creatine phosphokinase (CPK) as rare irritation to the muscle have been reported with statin treatment. The liver function studies will be utilized to rule out irritation to the liver and the urinalysis will screen for rhabdomyolysis. The lipid panel will assess that cholesterol and triglycerides remain within the normal range. Due to the processing requirements for the lipid panel, blood draws will be done while subjects are fasting. If there is any sign of myopathy, muscle pain or allergic reaction the medication will be discontinued. Pregnancy testing will only be conducted on female participants of child-bearing potential.

Safety Lab Tests

Chemistry	Hematology	Urinalysis
Creatine Kinase	Hemoglobin	pH
Potassium	Hematocrit	Color
Chloride	WBC	Clarity
Carbon Dioxide	RBC	Specific Gravity
BUN	MCV	Occult blood
Creatinine	MCH	Urobilinogen
Glucose	MCHC	Ketones

Calcium	RDW	Protein
Protein	MPV	Glucose
Albumin	Platelet Count	Pregnancy spot urine
ALP	Neutrophils	
AST	Lymphocytes	
ALT	Monocytes	
Bilirubin	Eosinophil	
Cholesterol	Basophils	
HDL cholesterol		
Triglycerides		
Serum Pregnancy (βHCG)		

In addition to the 7ml of blood for safety labs, we will collect approximately 30 ml of blood at each visit for biomarker analysis of immune function, MEK/ERK, RhoGTPase, and Ca2+ signaling, and cell activation.

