An independent data safety and monitoring board (DSMB) will be established and consist of 2 physicians who are not affiliated with the study but have significant expertise in conducting psychopharmacological interventions in children with FXS and/or autism. In addition, an independent statistician will be a member of the DSMB. The first DSMB will examine un-blinded adverse events and clinical data after six months from first subject enrolled into the clinical trial component to determine if the trial is safe to continue. DSMB meetings will be held annually thereafter until all subjects have completed the study. The investigators and staff will remain blinded throughout the trial unless there is an adverse event requiring unblinding, when medical treatment for a subject would be different based on whether or not they were receiving active study drug.

Any serious adverse events which occur to any subject after being randomized into this study and up until 30 days after the last dose of the study drug will be followed up for outcome and reported to the IRB according to their reporting guidelines. Mild and moderate adverse events considered related to the study medication, but not listed in the consent form will be reported to the IRB according to the reporting guidelines. Serious adverse events will be reviewed by the principal investigator for indications of a change in the overall risk assessment, or need for modification of the consent form.

Written standard operating procedures (SOPs) will be followed to ensure that the clinical trial component is conducted and data are generated, documented (recorded), and reported in compliance with the protocol, GCP, and the applicable regulatory requirements. Quality control (QC) will be applied to each stage of data handling. Monitoring, as defined in ICH GCP, Section 1.8, "The act of overseeing the progress of a clinical trial, and of ensuring that it is conducted, recorded, and reported in accordance with the protocol, SOPs, GCP, and the applicable regulatory requirement(s)" will be conducted throughout the conduct of the study.

The clinical investigator and the institution will permit trial-related monitoring, audits, IRB review, and regulatory inspection (FDA or other regulatory body) by providing direct access to source data/study documents.

15) Withdrawal of Subjects

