Half of the participants will receive the Parent-Implemented Language Intervention (PILI) under consent form A, the remaining half of participants will have the option to participate in the clinical trial portion of the study under consent form B, at which point they will be guaranteed to receive the PILI intervention.

All participants will receive the Parent-Implemented Language Intervention (PILI) under the clinical trial portion of the study, consent form B. In addition to PILI, half of the patients will be randomized to take lovastatin and may experience a beneficial response to lovastatin including heightened response to PILI with language improvements and reduction of problematic behaviors of FXS including ADHD,

aggression, and anxiety. All participants under consent form B will also benefit by receiving physical exams, cognitive assessments, and blood tests.

18) Vulnerable Populations

The patient population to be studied is developmentally disabled children with fragile x syndrome. We have done research with developmentally disabled and cognitively impaired individuals of all ages for many years. The consent process for individuals without the cognitive ability to consent will be completed by the parent, caregiver, or legally authorized representative (LAR), and no procedures will be done with any subjects without consent of either subject or parent/caregiver/LAR.

19) Sharing of Results with Subjects

At the conclusion of the study, the possible medical benefit from the study will be reviewed with the subject and his or her parent/guardian. Any laboratory work considered standard of care will be available for patients at their request. Psychological assessment scores may be communicated to the subjects if it does not impact future testing. If a subject has to be unblinded for emergency purposes then the subject will be notified by the principal investigator or study physician. Unblinding will be conducted in accordance with the MIND Institute's SOP# 500-014: Study Subject Unblinding Process. The results of the study may also be published or presented at scientific meetings including peer reviewed scientific journals that will be made publicly available through PubMed Central. In addition, after publication the results will be posted on the MIND Institute website under clinical trials

20) Setting

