The MIND Institute Research Clinic has a large waiting room with divided areas for each family, 10 examination rooms, a consult room, a chart/supplies room, a vitals room, and 2 coordinator stations totaling approximately 15,000 square feet. There are one-way mirrors and a state of the art digital video recording systems in each of the 4 observation rooms. It is in the clinical research space that subjects will be seen. We have a research phlebotomy lab adjacent to the patient evaluation rooms, where all blood samples will be drawn for this study. The private family rooms may be utilized for recruitment purposes and the MIND Institute also has many non-patient areas where subject phone contacts and study records can be stored.

The PILI assessments will be completed through secure video teleconferencing so families may complete the PILI in the comfort of their homes.

21) Resources Available

Drs. [name], [name], and [name] will follow patients through their treatment with the study drug, until they have completed the study. Designated qualified staff will conduct cognitive and behavioral assessments as required for the study. Coordinators and research assistants will be responsible for contacting and screening potential patients, scheduling and coordinating all patient appointments and visits, coordinating the processing of all samples, meeting with study monitors, as well as organizing all relevant supplies and data for the study. Transcriptionists will be

responsible for transcribing and coding all language samples for purposes of deriving the primary outcome measures. The number of physicians, coordinators, and raters is sufficient to successfully carry out the protocol to completion in the specified timeline. Study protocol specific training will occur and be documented prior to staff conducting assessments or procedures and all study staff will be approved and designated by the principal investigator.

The UC Davis Medical Center Investigational Drug Services pharmacy will store, over-encapsulate the active study medications, prepare the placebo capsules, and dispense the study drug.

22) Prior Approvals

All research staff will be required to complete CITI training per UCD research requirements and will be adequately trained to perform their allotted tasks as approved by the principal investigator.

23) Provisions to Protect the Privacy Interests of Subjects

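### Post-baseline lipid values are not masked, so Week 10 results could hint at the arm to whoever rates CGI-I at Week 20 or scores AE relatedness after Week 10

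*Combined protocol and SAP*

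**What the plan says.** **The drug.** Section 4 (Background) states: "Lovastatin is an inhibitor of the rate-limiting enzyme in cholesterol biosynthesis and an FDA-approved treatment for hyperlipidemia". The dosing rationale in Section 11(b) repeats the point: "Low doses of statins mainly affect cholesterol synthesis".

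**The measurement.** Section 11(b): "Safety labs, listed below, will be conducted at all three visits through the UC Davis health system pathology laboratory". The table lists cholesterol, HDL cholesterol and triglycerides. The stated purpose is: "The lipid panel will assess that cholesterol and triglycerides remain within the normal range". The visits are baseline, Week 10 and Week 20, so each child has a baseline value for comparison.

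**Use and access.** Section 14 uses the safety labs to judge whether a child may enter and stay in the study. Section 13 gives all study personnel access to study records and data. Section 16 has the study doctor discuss results that fall outside the normal range.

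**Blinding.** Section 14: "The investigators and staff will remain blinded throughout the trial", with an exception for adverse events that require unblinding. Section 28 leaves only the pharmacy unblinded to bottle contents.

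**The ratings.** Section 11(a) makes CGI-I a clinician rating that draws on parent history. The schedule table places it at Weeks 10 and 20, while the Section 11(a) text speaks of 3 and 6 months; the table is used here. The VAS and the ABC are completed by the parent or caregiver, and the ABC social avoidance subscale is the secondary endpoint. For adverse events, Section 11(b) says: "Each AE will be scored for severity, frequency, and relatedness to lovastatin". It does not say who scores them.

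**The concern.** A blinded trial is weakened when a routine test reflects the drug's own pharmacology and nothing controls who sees the result. Here the test is drawn before treatment and twice after it. The result is acted on during the trial, and the access rule as written does not exclude the people who make subjective judgements.

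The exposed measures are CGI-I at Week 20 and AE relatedness scored after Week 10. If a rater suspects the arm, expectation can move a global improvement score, and an ambiguous event may be more readily attributed to the drug. A difference found afterwards could be challenged on this ground, and the trial would have no data with which to answer.

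The protocol masks in other places. Language samples are coded by staff blind to hypotheses and participant characteristics (Section 11(a)), and the plasma samples for MMP-9 are coded until results are in (Section 11(b)). The lipid panel has no such protection.

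**Working it through.** The plan states no figure on this point, so there is none to reproduce. The check has two parts: whether the text leaves the route open, and how informative a lipid pair could be.

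**1. The route, link by link**

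- *Does the drug act on lipids?* Yes, by the documents' own account (Sections 4 and 11(b)).
- *Is there a before/after pair?* Yes: baseline against Week 10, and again against Week 20.
- *Does someone read the values during the trial?* Yes. Sections 14 and 16 require it, and the only reader named is the study doctor. The DSMB cannot be the per-visit reader: it first meets six months after the first enrolment and then annually, while each child is treated for 20 weeks.
- *Are raters kept from the values?* No passage says so, and Section 13 gives all study personnel access.
- *Are the CGI-I rater and AE scorer the same people as the lab reader?* Not stated.
- *Which panel matters?* Labs and ratings share visits. Unless results return before the ratings are made, which the documents do not say, a panel cannot affect ratings at its own visit. The realistic path is the Week 10 panel acting on Week 20 CGI-I and on AE scoring after Week 10.
- *Do parents see values?* Section 16 covers only out-of-range results. Section 19 covers standard-of-care labs in a passage about the end of the study. Neither gives families routine mid-trial values.

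**2. How informative one pair could be (assumptions only)**

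Assume the percent change in cholesterol is normal with the same SD in both arms and mean zero on placebo. Let d = assumed percent fall / SD of percent change. Then:

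- accuracy of the best single cut = Φ(d/2)
- AUC = Φ(d/√2)

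| Assumed fall | Assumed SD | d | Correct guesses | AUC |
|---|---|---|---|---|
| 10% | 15% | 0.67 | Φ(0.33) = 63% | 0.68 |
| 15% | 10% | 1.5 | Φ(0.75) = 77% | 0.86 |
| 25% | 10% | 2.5 | Φ(1.25) = 89% | 0.96 |

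Chance is 50%. These are ceilings for a reader of that one pair, who would have to know both distributions and apply the best cut.

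**3. What it would take to matter**

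Suppose a rater's score differs by b SD according to the guessed arm. The spurious arm difference is then b × (2 × accuracy − 1) SD. With 50 children taken as 25 per arm, the standard error is √(2/25) = 0.283 SD. For a two-sided 0.05 normal test with no true effect:

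- b = 0.2, d from 0.5 to 3: false-positive rate 5.2% to 9.4%
- b = 0.4, same d: 5.9% to 23.2%
- b = 0.6, same d: 7.0% to 45.1%

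For example, b = 0.4 and d = 3 give accuracy 0.933, a bias of 0.4 × 0.866 = 0.347 SD, and 0.347/0.283 = 1.23 standard errors. Both b and d are assumed, and the calculation supposes that the rater sees every child's lipids. It shows when the problem would be small or material; it does not predict what will happen.

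**The case against.** A reader might infer that lipid reports go to the clinicians who rate CGI-I and AE relatedness. The documents do not support that. Section 21 says the study physicians "will follow patients through their treatment with the study drug, until they have completed the study", but it also assigns cognitive and behavioral assessments to designated staff and counts raters separately from physicians. The AE sentence is passive. Overlap is permitted, not shown.

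A reader might also infer that parents learn the arm, so that the secondary endpoint cannot be separated from expectation. That is too strong. Section 19 does say "Any laboratory work considered standard of care will be available for patients at their request", but the section opens with the end of the study and the sentence covers standard-of-care work, not protocol safety labs. A fall that stays within range prompts no conversation under Section 16. Parents would be reached only if staff conveyed a guess or an out-of-range value was discussed.

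The accuracy figures have no source in the documents for the fall or the SD, and clinicians glancing at a report will do worse than an optimal rule. At the low end the false-positive rate is nearly nominal. CGI-I and VAS are exploratory, and scoring of the primary composite is largely protected.

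All of this stands and limits the point. What remains is that following the access rule as written leaves an arm-related value open to people whose judgements depend on the blind, and no text prevents it.

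**Conclusion.** The point holds as a cheap improvement to the safeguarding of the blind, not as evidence that the blind fails. The gap is specific: lipid values related to the drug's known action, read during the trial, open to all study personnel, with no masking after baseline. The exposure is the Week 10 panel acting on Week 20 CGI-I and on later AE relatedness. The ABC and VAS are exposed only indirectly, and primary outcome coding is done by separate blinded staff.

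The size of the risk is unknown. The 63% to 89% range rests wholly on assumed standardized shifts of 0.67 to 2.5 and on an ideal reader, and it is not a measure of bias in any endpoint. The risk is minor if either the lipid shift or the rater's response is small, and material only if both are at least moderate and the rater actually sees the values.

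**What to change.** Keep the panel and its timing. Amend Sections 11(b), 13 and 14 to state that:

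- post-baseline lipid values are withheld from CGI-I raters, AE-relatedness scorers and families until the trial is unblinded, as an exception to the general access rule;
- an existing study physician who makes none of these ratings reviews them (Section 21 describes more than one physician following the children);
- only safety flags, under criteria the investigators set in advance, are passed to the team;
- the roles that rate CGI-I and score AE relatedness are named.

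Reconcile the out-of-range conversation in Section 16 with this routing, and say in Section 19 that study lab results are released after unblinding. Asking raters and parents to record a guess of the arm at Week 20 would show whether the blind held.

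The cost is a few sentences and one extra handling step for lipid results, with no new staff if roles are split among the existing physicians. Some leakage remains: a flagged value can itself suggest an arm, and CK and transaminases, which Section 16 says lovastatin may raise, stay visible to the team for safety.
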